CLINICAL PROTOCOL

409 **Aim 1.1** the superiority of the PF over Sensor-augmented mode (SAM) in controlling GV. PF is a
410 system designed to provide patients with *actionable information* about glucose control in general
411 and GV in particular (e.g. estimated HbA1c (eA1c), risk of hypoglycemia, and activity level);

412 **Aim 1.2** the superiority of the DSS over SAM in controlling GV. DSS is a CGM-based system that
413 includes PF and further assists with treatment recommendations for common metabolic
414 challenges;

415 **Aim 1.3** the overall non-inferiority of DSS over PF intervention to control GV and superiority of
416 DSS to maintain tight glycemic control over time (lower variations of GV in time).

417 **Aim 2 (personalization of treatment policy)** We hypothesize that the participants in this study
418 will have technology intervention preferences (e.g. PF or DSS) that can be predicted by key
419 psychosocial and behavioral parameters and are prognostic of the level of GV control achievable
420 by the intervention. We will:

421 **Aim 2.1** confirm that technology acceptance and trust are predictive of the level of GV control
422 achieved during the study (see Aim 1), regardless of the type of DSS system in use. We
423 hypothesize that technology acceptance will correlate negatively with GV: i.e. higher technology
424 acceptance leads to lower GV;

425 **Aim 2.2** explore the impact of technology expectations and experience on the performance of
426 each type of technology intervention (SAM, PF, DSS). For example, higher expectation will
427 negatively correlate with GV for the SAM treatment, but not the DSS treatment.

428 **Aim 2.3** assess the correlation between relevant psycho-behavioral traits with the performance
429 of PF vs DSS, identifying potential pathways to the corresponding optimal technology-based
430 treatment policies.

431 **1.3. Outcomes**

432 **1.3.1. Glycemic outcomes**

433 The primary outcome of this study will be Glucose Variability (GV) as measured by CGM-based
434 Coefficient of Variation (CV), as recommended by the International Consensus on Use of
435 Continuous Glucose Monitoring. To further characterize glucose control, we will compute other
436 CGM Consensus outcomes as well:

437 Average

438 Percent in different ranges:

439 ○ <50 mg/dL

440 ○ <54 mg/dL

[figure not shown]
CLINICAL PROTOCOL

- 441 ○ <60 mg/dL
- 442 ○ <70 mg/dL
- 443 ○ ≤70-≤180 mg/dL
- 444 ○ >180 mg/dL
- 445 ○ >250 mg/dL
- 446 ○ >300 mg/dL

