1653 Sample size determination is based on our related pilot studies of DSS. We estimate that the
1654 effect size of DSS vs. SAM will be $f^2=0.22$. Power calculations (G*Power 3.1.9.2) assuming $\alpha=0.017$
1655 (corrected for multiple comparisons), 95% power, correlation of 0.55 between the repeated
1656 measures, and attrition of 20%, yield a sample size of N=100 subjects to be randomized at
1657 baseline, with N=80 subjects completing the study. PF vs. SAM assumes the same effect size. We
1658 expect that while overall DSS effect vs. PF will be smaller than vs. SAM, GV control over time will
1659 be more consistent. Aim 1.3 analysis therefore assumes a small effect size (0.15) but 5 repeated
1660 measures (bi-weekly) in each condition with higher correlation (0.65), leading to an achieved
1661 power of 97.2% for this Aim.

1662 **14.2.2. Exploration of the effect of treatment escalation vs. de-escalation:**

1663 A key advantage of the proposed study design (beyond the optimal statistical power) is the
1664 possibility to explore the glucose control and psycho-behavioral impact of features being added
1665 and/or enhanced with prescriptive components (DSS), vs. features being limited to information
1666 (PF) or even removed (SAM). We will perform this analysis by looking at the between factors in
1667 the repeated ANOVA analysis, contrasting the escalation group vs. de-escalation group. While

CLINICAL PROTOCOL

1668 not powered, this analysis will provide key insights in the future feature adaptation schemes
1669 based on the ATI.

1670 **14.3. Outcome Measures**

1671 **14.3.1. Glycemic outcomes:**

1672 The primary outcome of this study will be Glucose Variability (GV) as measured by CGM-based
1673 Coefficient of Variation (CV), as recommended by the International Consensus on Use of
1674 Continuous Glucose Monitoring. To further characterize glucose control, we will compute other
1675 CGM Consensus outcomes as well:

- 1676 • Average
- 1677 • Percent in different ranges:
 - 1678 ○ <50 mg/dL
 - 1679 ○ <54 mg/dL
 - 1680 ○ <60 mg/dL
 - 1681 ○ <70 mg/dL
 - 1682 ○ ≤70-≤180 mg/dL
 - 1683 ○ >180 mg/dL
 - 1684 ○ >250 mg/dL
 - 1685 ○ >300 mg/dL
- 1686 • SD and coefficient of variation
- 1687 • LBGI, HBGI, ADRR

1688 Each modality of treatment will be assessed using the last 4 weeks of CGM recordings, as we
1689 expect most of the GV benefits of each intervention to be realized within the first 4 weeks of the

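### Aim 1 words four claims against a flat 0.017 that fits three; name the confirmatory family and margin, and use Holm at a stated, small cost

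*Combined protocol and SAP*

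**What the plan says.** Section 1.2 gives Aims 1.1 and 1.2 one superiority claim each: PF over SAM and DSS over SAM on glucose variability. Aim 1.3 holds two claims in one sentence, "the overall non-inferiority of DSS over PF intervention to control GV and superiority of" DSS in holding control steady over time. No non-inferiority margin is given.

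Section 14.2.1 states the threshold of 0.017 with the words "corrected for multiple comparisons), 95% power, correlation of 0.55 between the repeated" measures. It does not name the method, the number of comparisons or the family. It adds that "PF vs. SAM assumes the same effect size". For Aim 1.3 it assumes an effect of 0.15 and five repeated "measures (bi-weekly) in each condition with higher correlation (0.65), leading to an achieved" power of 97.2%.

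Section 14.3.2, the analysis section, repeats no threshold and names no multiplicity procedure. It describes the bi-weekly, five-measure analysis for Aim 1.3 as exploring how outcomes evolve.

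**The concern.** The plan says its threshold is corrected, but the count behind the correction does not match the count of claims. Three shares of 5% cover Aims 1.1 and 1.2 and only one of the two parts of Aim 1.3. The part that received a power calculation is the over-time comparison; the non-inferiority part has neither power nor margin. Section 14.2.2 labels the escalation comparison as not powered. The over-time claim gets the opposite treatment in 14.2.1, so it cannot simply be assumed to be exploratory.

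Two things are at stake. If all four claims are confirmatory, 5% family-wise control is not guaranteed. And because the correction appears only as a sample-size input, the analyst has no written decision rule. A flat 0.05/3 is also less powerful than a stepwise rule over the same three tests. This matters most for the smaller contrasts.

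**Working it through.** **Inputs from 14.2.1.** Effect 0.22, α = 0.017, power 95%, correlation 0.55, 80 completers of 100 randomized. For Aim 1.3: effect 0.15, five measures, correlation 0.65, power 97.2%. Sidedness is not stated; I take the tests as non-directional F tests.

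**Reproducing the plan.** For a within-subject factor with m levels, the noncentrality is λ = f²·N·m/(1−ρ), on m−1 and (N−1)(m−1) degrees of freedom.

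- DSS vs SAM: λ = 0.22² × 80 × 2 / 0.45 = 17.2, giving 95.4% power at 0.017. For 95%, 79 completers are needed; 79/0.8 = 98.75, so 99 randomized. The stated 80 and 100 are reproduced. The text prints "effect size of DSS vs. SAM will be $f^2=0.22", but only f = 0.22 gives this N; f² = 0.22 would need 20.
- Over-time test: λ = 0.15² × 80 × 5 / 0.35 = 25.7, giving 97.2% at 0.017. The stated figure is reproduced, so it belongs to the over-time analysis and was computed at the same threshold.

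**Error rate.**

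- 0.05/3 = 0.0167, printed as 0.017. Three tests: 3 × 0.017 = 5.1%.
- Four tests: 4 × 0.017 = 6.8%; if independent, 1 − 0.983⁴ = 6.6%.
- With a positive margin, PF = SAM and DSS = SAM together imply DSS = PF, so the non-inferiority null is then false. At most three of the four nulls hold at once, and the bound returns to 5.1%.
- With the margin shrunk to zero and non-inferiority tested one-sided at half the level, simulation gives about 5.4% to 5.5%.

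**Power at each candidate first step (N = 80).**

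| Threshold | DSS-SAM | Over-time |
|---|---|---|
| 0.017 (plan) | 95.4% | 97.2% |
| 0.0167 (Holm over three) | 95.3% | not in family |
| 0.0125 (Holm over four) | 94.2% | 96.4% |

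For 95% at 0.0125, 83 completers are needed (83/0.8 = 103.75, so 104 randomized).

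**Power on a smaller contrast.** Simulation with N = 80 and correlation 0.55. DSS-SAM is 0.44 SD (2 × 0.22), and PF-SAM is assumed to be half that, 0.22 SD. DSS-PF is modelled as a two-sided difference, and the over-time test as independent of the rest.

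| Rule | PF-SAM | DSS-SAM |
|---|---|---|
| Flat 0.017 | about 36% | about 95% |
| Holm over three | about 46% | about 95% to 96% |
| Holm over four, over-time effect real | about 46% | about 96% |
| Holm over four, over-time effect null | about 38% | about 94% |

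If DSS-PF is instead tested for non-inferiority with assumed margins of 0.11 to 0.22 SD, Holm over three gives PF-SAM about 52% to 53%, with DSS-SAM at about 96% to 97%. These margins are assumptions, as the plan states none.

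**A lone real effect.** With one planned effect real and three independent nulls, Holm over four gives 94.1% and the flat rule 95.3%, a loss of about 1.2 points.

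**The case against.** The strongest reply is that the plan is coherent as three numbered aims sharing 5%. Section 14.3.2 describes the over-time analysis as exploration, and 14.2.1 gives one power figure for Aim 1.3 as a whole. On that reading 0.05/3 is right, and the three pairwise contrasts at 0.017 have a simulated family-wise error of about 4.5%. This stands as a possible reading. It does not settle the matter, because section 1.2 calls the over-time part superiority and 14.2.1 powers it. The documents conflict and the sponsor has to choose.

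A reader might infer that Holm over all four claims restores error control and raises power at no cost. The figures do not support that. Holm over four dominates a flat 0.0125, not the plan's 0.017, because its first step is stricter. It loses about 1.2 points when one effect is real, and most of its gain on PF-SAM disappears if the over-time effect is null.

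A reader might also take 6.8% as the actual error rate. It is an upper bound that a positive margin makes unattainable.

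Finally, a power gain for DSS-PF tested as a two-sided difference says nothing about Aim 1.3, which claims non-inferiority. Power for that claim cannot be computed, nor can the claim enter Holm, until a margin is stated.

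**Conclusion.** The concern holds in a limited form and is minor. Aim 1 words four claims, the threshold fits three, and the plan names neither its confirmatory family nor a testing procedure for the analysis. If all four are confirmatory, 5% control is not guaranteed, but the likely excess is between nothing and about one point, depending on the unstated margin.

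A stepwise rule is a real improvement whose cost depends on the family. Over three claims it is never less powerful than flat 0.05/3; against the rounded 0.017 it gives up about 0.1 point at the first step. Over four claims it trades about 1.2 points for a lone effect against gains when several effects are real.

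The power figures assume f = 0.22, 80 completers, correlation 0.55, non-directional tests and, for the smaller contrast, PF at half the DSS effect. Section 14.2.1 itself assumes equal effects for PF and DSS against SAM; the half-effect case is a sensitivity scenario.

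**What to change.** In section 14.3.2:

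1. State whether the over-time part of Aim 1.3 is confirmatory or exploratory, and word section 1.2 to match.
2. State the non-inferiority margin for DSS against PF, with its justification and the sidedness of that test.
3. Replace the flat threshold with Holm at family-wise 5%.
   - Over-time claim exploratory: Holm over three (0.0167, 0.025, 0.05).
   - All four confirmatory: Holm over four (0.0125, 0.0167, 0.025, 0.05).

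In section 14.2.1, name the family and procedure behind the threshold. For Holm over three, give it as 0.0167. For Holm over four, restate first-step power at 80 completers as 94.2% for DSS-SAM and 96.4% for the over-time test. Add the power for non-inferiority once the margin is fixed.

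The cost is a short text change plus the work of justifying a margin. No extra participants are needed if 94.2% at the first step is accepted; holding 95% there would take 104 randomized instead of 99 on the same calculation. The change should be made before any outcome data are analysed by modality.

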836 Once all training activities are completed, the participant will be given adequate supplies and
837 study devices to last until the subsequent clinic visit. An appointment for Visit 4 will be scheduled

838 **6.3. Home Use of DiAs in Phase 1 Mode**

839 The participant will complete a minimum of 8 weeks of DiAs use in Phase 1 Mode at home. During
840 the course of Phase 1, participants will complete EMA surveys and post-phase questionnaires.

841 **6.3.1. Phase 1 EMA Surveys**

842 Over the course of 2-3 days every two weeks of Phase 1, the participant will be asked to complete
843 a “Daily Diary” with 3-5 entries of 3-4 questions each day, for a minimum total of 48 entries per
844 participant during each Phase.

845 **6.3.2. Post-Phase 1 Questionnaires Week 7**

846 Participants randomized to escalation will be sent the following questionnaires on week 7 (day
847 42 of Phase 1) and will be asked to complete them within 1 week:

- 848 • Pittsburgh Sleep Quality Index

CLINICAL PROTOCOL

- 849
- Hyperglycemia Avoidance Scale

850 **6.3.3. Post-Phase 1 Questionnaires Week 8**

851 Participants randomized to escalation will sent the following questionnaires on week 8 (day 49
852 of Phase 1) and will be asked to complete them within 1 week:

- 853
- Confidence in Diabetes Self-Care Scale
- 854
- T1-Diabetes Distress Scale
- 855
- Hypoglycemia Fear Survey

856 **6.4. Visit 4 – Phase 2 Initiation**

857 All participants in each randomization scheme use PF in Phase 2. Phase 2 initiation may be
858 conducted either via web conference or an office visit. The participant will remotely receive a
859 mode change for Phase 2. Study staff will review the features of the Personalized Feedback (PF)
860 mode and answer any questions. Participant will have a blood/urine pregnancy test that must be
861 negative in order to continue to participate in this study.

862 **6.4.1. Training on Phase 2 DiAs Mode**

863 The participant will be trained on the following features of the Personalized Feedback System:

- 864
- **Tracking of estimated HbA1c:** When properly calibrated, eA1c is within 0.3% of
865 reference HbA1c on average, and within 1% of HbA1c >95% of the time.
- 866
- **Hypoglycemia Risk Indicator:** Provides an indication of the current risk for
867 hypoglycemia.
- 868
- **Insulin Sensitivity Profile & Indicator:** Tracks changes in insulin sensitivity (SI) and
869 creates daily and monthly SI profiles.
- 870

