1620 **Chapter 13 Miscellaneous Considerations**

1621 **13.1. Prohibited Medications, Treatments, and Procedures**

1622 Participants using glulisine at the time of enrollment will be asked to contact their personal
1623 physician to change their prescribed personal insulin to lispro or aspart for the duration of the
1624 trial.

1625 The study devices (study insulin pump, study CGM) must be removed before Magnetic Resonance
1626 Imaging (MRI), Computed Tomography (CT) or diathermy treatment. Participants may continue
1627 in the trial after temporarily discontinuing use if requiring one of the treatments above.

1628 **13.2. Participant Withdrawal**

1629 Participation in the study is voluntary. Participant may withdraw at any time. For participants
1630 who do withdraw from the study, the study team will determine if their data will be used in
1631 analysis.

1632 **13.3. Confidentiality**

1633 For security and confidentiality purposes, subjects will be assigned an identifier that will be used
1634 instead of their name. Protected health information gathered for this study may be shared with
1635 the third-party collaborators. De-identified subject information may also be provided to
1636 collaborators involved in the study after the appropriate research agreement has been executed.

1637 **Chapter 14 Statistical Consideration**

1638 **14.1. Design and Randomization**

1639 This is a randomized crossover study in T1DM designed to demonstrate the efficacy of
1640 personalized feedback (PF) and decision support (DSS) over sensor-augmented pump (SAM)
1641 therapy and to establish relationships between the level of glucose variability (GV) control
1642 achievable by the intervention and individual psycho-behavioral characteristics.

1643 We plan to split the study into 4 cohorts of about 25 participants each (expected retention 20
1644 per cohort). Each cohort will continue for ~7 months and will have the structure presented in
1645 Figure 5. Following recruitment, screening, and a run-in period of SAM, participants will be
1646 randomized into one of two groups: escalation vs. de-escalation of devices and function. Each
1647 treatment modality (SAM, PF, DSS) will continue for about 8 weeks, with the last 4 weeks used
1648 to assess GV from CGM data.

1649 **Escalation: SAM → PF → DSS**

1650 **De-escalation: DSS → PF → SAM**

1651 **14.2. Sample Size**

1652 **14.2.1. Sample Size Determination:**

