1690 intervention, and a minimum of 24 days of data is considered optimal for CGM-based CV
1691 determination.

1692 **14.3.2. Glucose Variability Reduction Achieved with CGM-based expert systems:**

1693 General linear models (GLM) (repeated measures ANOVA) will be used to assess the significance
1694 of the differences in average response between SAM, PF, and DSS across appropriate CGM-based
1695 metrics. The particular design of the clinical study allow for Aims 1.1, 1.2, and 1.3 to each be
1696 addressed independently in a randomized crossover analysis, as shown in Figure 4. While the
1697 randomized order of the interventions (escalation vs de-escalation) allows for an objective
1698 assessment of the average efficacy of each of them, we will introduce the order as a fixed factor
1699 to verify if significant study effects can be detected. Finally, we will study the evolution of GV
1700 within each modality period: GV and other CGM-based outcomes will be computed bi-weekly
1701 (the minimum length of time for precise GV assessment) and entered in a repeated measures

CLINICAL PROTOCOL

1702 GLM analysis; within-subject contrast (linear and polynomial) using 5 repeated measures per
1703 condition to explore the evolution of the glycemic outcomes in time; Aim 1.3.

1704 **14.4. Exploration of the effect of treatment escalation vs. de-escalation**

1705 A key advantage of the proposed study design (beyond the optimal statistical power) is the
1706 possibility to explore the glucose control and psycho-behavioral impact of features being added
1707 and/or enhanced with prescriptive components (DSS), vs. features being limited to information
1708 (PF) or even removed (SAM). We will perform this analysis by looking at the between factors in
1709 the repeated ANOVA analysis, contrasting the escalation group vs. de-escalation group. While
1710 not powered, this analysis will provide key insights in the future feature adaptation schemes
1711 based on the ATI.

1712 **14.5. Psychological and Behavioral Questionnaires**

1713 *Quantitative* data on usability and satisfaction will be analyzed using simple descriptive statistics.
1714 In addition, we will analyze scores from the measures in the psychosocial assessment battery to
1715 determine if changes occur over time and between groups. Using SPSS 26, we will construct
1716 predictive models in the general linear modeling (GLM) framework to examine each set of

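### The 97.2% power for Aim 1.3 assumes five two-week measures per condition, but an 8-week phase holds four; with four, the time-effect power is 94.1%

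*Combined protocol and SAP*

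**What the plan says.** - **Power (14.2.1).** Aim 1.3 is given a small effect size of 0.15, with five repeated "measures (bi-weekly) in each condition with higher correlation (0.65), leading to an achieved" "power of 97.2% for this Aim". The section works with alpha 0.017 and 80 completers.
- **Analysis (14.3.2, repeated in 1.3.2).** The evolution of glucose variability (GV) is to be studied "within each modality period: GV and other CGM-based outcomes will be computed bi-weekly". Two weeks is described as "the minimum length of time for precise GV assessment) and entered in a repeated measures" "GLM analysis; within-subject contrast (linear and polynomial) using 5 repeated measures per" condition.
- **Phase length.** Section 14.1 says each "treatment modality (SAM, PF, DSS) will continue for about 8 weeks, with the last 4 weeks used" for the GV assessment. The visit schedule gives each phase 8 weeks at home. Section 6.3 says "The participant will complete a minimum of 8 weeks of DiAs use in Phase 1 Mode at home", and sections 6.5, 6.7, 7.3, 7.5 and 7.7 set the same minimum.
- **Overall duration.** Section 1.2 describes a 6-month crossover. On the cohort, 14.1 says "Each cohort will continue for ~7 months and will have the structure presented in" Figure 5.
- **Aim 1.3 (1.2).** It has two parts: overall non-inferiority of DSS to PF on GV, and superiority of DSS in keeping GV steady over time.

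**The concern.** The number of measures and the phase length do not fit together. Windows of at least two weeks, taken inside an 8-week phase, give four measures. The power statement and the planned contrasts both use five.

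Two things are at stake. First, the number of measures enters the power formula directly, so the stated 97.2% is not what the planned phases deliver. Second, the analyst will have to settle the number of time points once data are in hand: drop to four, overlap windows, or borrow one from the run-in or the preceding mode. That choice also fixes the available polynomial contrasts, which go up to quartic with five points and cubic with four. It is better made in advance.

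A smaller matter is scope. The 97.2% is given for the whole Aim, although it reproduces only as a test over time.

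**Working it through.** **Windows per phase.** 8 weeks / 2 weeks = 4. Five windows need 5 × 2 = 10 weeks per phase.

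**Inputs for power (all from 14.2.1).** Effect size 0.15, taken as Cohen's f; correlation between repeated measures 0.65; alpha 0.017; N = 80 completers; m = 5 measures. The section names G*Power but not the test. Sphericity (epsilon = 1) is my assumption.

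**Formula (repeated-measures ANOVA, one-sample within-subject time effect).**

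- noncentrality: lambda = epsilon × f² × N × m / (1 − rho)
- df1 = epsilon × (m − 1)
- df2 = epsilon × (N − 1)(m − 1)
- power = probability that a noncentral F(df1, df2, lambda) exceeds the central F critical value at alpha 0.017

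**Reproducing the plan's figure, m = 5.** lambda = 0.0225 × 80 × 5 / 0.35 = 25.71; df = 4 and 316; critical F = 3.06; power = 97.21%. This matches the stated 97.2%.

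The match depends on these inputs. With m = 5, N = 100 gives 99.4% and alpha 0.05 gives 99.0%. With N = 80 and alpha 0.017, m = 10 gives 99.96%. Reading 0.15 as f² gives about 100%.

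**Same inputs, m = 4.** lambda = 0.0225 × 80 × 4 / 0.35 = 20.57; df = 3 and 237; critical F = 3.46; power = 94.07%, or 94.1%. The loss is 97.2 − 94.1 = 3.1 points.

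**Sensitivity to sphericity.** The documents give no epsilon, so the values below 1 are illustrations.

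| epsilon | five measures | four measures |
|---|---|---|
| 1.0 | 97.2% | 94.1% |
| 0.9 | 95.8% | 91.8% |
| 0.8 | 93.7% | 88.8% |

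A departure from sphericity lowers both columns. The effect of the missing measure is the gap between them: 3.1 points at epsilon 1, 4.0 at 0.9 and 4.9 at 0.8.

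**Calendar.** Five windows in each of three phases need 3 × 10 = 30 weeks, or 32 to 34 with the 2-4 week run-in. As planned it is 3 × 8 = 24 weeks, or 26 to 28 with run-in. Six months is about 26 weeks; seven months is about 30.

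**The case against.** **A fifth measure may have been intended.** The documents never say that windows must not overlap, the stated 8 weeks is approximate or a minimum, and Figures 4 and 5 are not shown in the text available. This stands in part: the origin of a fifth point cannot be wholly excluded, and the fix should allow for it. But no section describes overlapping windows or a longer phase, and a minimum length permits an overrun without planning one.

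**A week-0 window could supply it.** For the escalation group the SAM run-in directly precedes the SAM phase in the same mode, so there a week-0 point would be measured under SAM. That does not help Aim 1.3, which concerns DSS and PF. A window before either of those belongs to a different mode and lies outside the period.

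**The calendar does not rule out five.** This is largely right for the cohort duration: 32 weeks is about 7.4 months, close to the approximate 7 months stated. The 8-week entries in the schedule and the 6-month crossover are the better evidence.

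**Stronger readings that the documents do not support.**

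- A reader might carry 94.1% over to a DSS versus PF condition-by-time interaction. Getting that value from the interaction formula requires two independent groups totalling 80. Here every completer receives both modes, so that test needs its own within-subject calculation.
- A reader might conclude that the analysis in 14.3.2 cannot be run. It can be run with four points, or with five once a window is defined; what is missing is the definition.
- A reader might conclude that the trial is underpowered. The main sample-size calculation does not use the five measures, and 94.1% is still good power.

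**Conclusion.** The inconsistency is real and minor. Sections 1.3.2, 14.2.1 and 14.3.2 call for five two-week measures per condition, while the planned phase holds four non-overlapping ones and no source for a fifth is given. On the plan's own inputs, the power for the within-subject time effect falls from 97.2% to 94.1%, just below the 95% set for the main comparison.

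This rests on reading 0.15 as f (the reading that reproduces the plan's figure), 80 completers, sphericity and non-overlapping windows. It covers the time effect only. Neither figure is the power of the overall DSS versus PF non-inferiority comparison in the same Aim, although the wording of 14.2.1 could be taken that way. Section 14.3.2 presents the analysis as exploring change over time, which also keeps the consequence small.

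**What to change.** 1. In 1.3.2, 14.2.1 and 14.3.2, change five repeated measures per condition to four.
2. In 14.2.1, replace the 97.2% with 94.1%, described as the power for the within-condition time effect (f=0.15, sphericity assumed).
3. Add a sentence there that this figure is not the power of the overall DSS versus PF non-inferiority comparison. Do not attach it to a condition-by-time interaction; if that test is wanted, calculate its power with condition as a within-subject factor.
4. If a fifth measure was intended, define its window within the phase instead of making changes 1 and 2, and keep 97.2% for the time effect. Change 3 still applies.

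The cost is wording. N stays at 80 completers and 100 randomized, and visits and phase length are unchanged. With four measures, the stated power for Aim 1.3 becomes about 3 points less favourable.
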